10.1.9.1.2 FILE MANAGEMENT AT THE TRIAL CENTER

It is the responsibility of the Investigator to ensure that the trial center file is maintained in accordance with ICH Guidance for Industry E6 Good Clinical Practice: Consolidated Guidance, Section 8 – Essential Documents for the Conduct of a Clinical Trial. Documentation is subject to inspection by the sponsor and relevant regulatory agencies.

10.1.9.2 RECORDS RETENTION AT THE TRIAL CENTER

It is a sponsor requirement that all Investigators participating in clinical studies maintain detailed clinical data for one (1) of the following periods:

- Country-specific requirements, or
- A period of at least two (2) years following the last approval of a marketing application approved by a Regulatory Authority in an ICH region or until there are no pending or contemplated marketing applications in an ICH region, or,
- A period of two (2) years after Revance notifies the Investigator that the data will not be submitted for review by any Regulatory Authority

10.1.9.3 TREATMENT OF MISSING DATA

Some data elements will be missing in this study due to subjects who withdraw from the study, subjects who are lost to follow-up, or subjects who do not complete all study visits. The completion status of each subject will be documented (e.g., completed protocol, withdrew from study, lost to follow-up, etc.). All reasonable efforts will be made by the study staff to maintain contact with the study participants during their participation in the study. The study coordinator will attempt to contact any subjects who are lost to follow-up. For subjects who are unwilling to return to clinic for follow-up, the study coordinator will attempt to contact them and to collect study data from them during a telephone call or by forms sent to them through the mail.

10.1.10 PROTOCOL DEVIATIONS

This trial will be conducted as described in this protocol, except for an emergency situation in which the protection, safety, and well-being of the subject requires immediate intervention, based on the judgment of the Investigator (or a responsible, appropriately trained professional designated by the Investigator). In the event of a significant deviation from the protocol due to an emergency, accident, or mistake, the Investigator or designee must contact Revance at the earliest possible time by telephone. This will allow

an early joint decision regarding the subject's continuation in the trial. This decision will be documented by the Investigator and the Sponsor.

[REDACTED]

[REDACTED]

[REDACTED]

[REDACTED]

[REDACTED]

[REDACTED]

[REDACTED]

[REDACTED]

[REDACTED]

[REDACTED]

[REDACTED]

[REDACTED]

[REDACTED]

[REDACTED]

[REDACTED]

[REDACTED]

[REDACTED]

[REDACTED]

[REDACTED]

[REDACTED]

[REDACTED]

[REDACTED]

10.2 ADDITIONAL CONSIDERATIONS

10.2.1 ETHICS AND RESPONSIBILITY

This trial must be conducted in compliance with the protocol, the ICH Guidance for Industry E6 Good Clinical Practice: Consolidated Guidance and the applicable regulatory requirements. Investigators must submit all essential regulatory documentation, as required by local and national regulations (including approval of the protocol and informed consent form by an HHS-registered IRB/IEC) to Revance before investigational product will be shipped to the study site.

[REDACTED]

[REDACTED]

[REDACTED]

[REDACTED]

[REDACTED]

[REDACTED]

[REDACTED]

[REDACTED]

[REDACTED]

[REDACTED]

[REDACTED]

- [REDACTED]
- [REDACTED]
- [REDACTED]

[REDACTED]

[REDACTED]

10.3 ABBREVIATIONS

| | |
|---------|--|
| AE | Adverse Event |
| ANCOVA | Analysis of Covariance |
| AOFAS | American Orthopaedic Foot and Ankle Score |
| BoNTA | Botulinum Toxin Type A |
| BP | Blood Pressure |
| CFR | Code of Federal Regulations |
| cm | Centimeter |
| CRF | Case Report Form |
| CS | Clinical Significant |
| DMC | Data Management Committee |
| EC | Ethics Committee |
| ECG | Electrocardiogram |
| FADI | Foot and Ankle Disability Index |
| FDA | Food and Drug Administration |
| GCP | Good Clinical Practice |
| GLP | Good Laboratory Practices |
| GMP | Good Manufacturing Practices |
| HHS | Health and Human Services |
| HR | Heart Rate |
| IB | Investigator's Brochure |
| ICH | International Council for Harmonisation |
| IM | Intramuscular(ly) |
| in | Inch |
| IND | Investigational New Drug Application |
| IRB | Institutional Review Board |
| ITT | Intention-To-Treat |
| kDA | Kilodalton |
| MedDRA | Medical Dictionary for Regulatory Activities |
| mL | Milliliter |
| mm | Millimeter |
| msec | Millisecond |
| NCS | Not Clinically Significant |
| ng | Nanogram |
| NIH | National Institutes of Health |
| OHRP | Office for Human Research Protections |
| PFPS | Plantar Fasciitis Pain and Disability Scale |
| PP | Per Protocol |
| PROMIS | Patient Reported Outcome Measurement Information System |
| QT | Measurement of time between start of the q wave and the end of the t wave in the heart's electrical conduction |
| QTc | Corrected QT interval; represents electrical systole |
| Revance | Revance Therapeutics, Inc. |
| RT002 | DaxibotulinumtoxinA for Injection |
| RTP004 | Revance absorption enhance peptide |
| SAE | Serious Adverse Event |
| SC | Subcutaneous |

| | |
|-------|------------------------------------|
| SoA | Schedule of Assessments |
| SOP | Standard Operating Procedure |
| SPT | Serum Pregnancy Test |
| TdP | Torsade de Pointe |
| U | Units (botulinum toxin) |
| UA | Urinalysis |
| UPT | Urine Pregnancy Test |
| US | United States of America |
| VAS | Visual Analog Scale |
| WFBMC | Wake Forest Baptist Medical Center |
| WOCBP | Women of Child-Bearing Potential |

SPT	Serum Pregnancy Test
UPT	Urine Pregnancy Test
US	United States of America
VAS	Visual Analog Scale
WOCBP	Women of Child-Bearing Potential

1 INTRODUCTION

Ten percent of the general population experiences heel pain or plantar fasciitis during their lifetime.⁽¹⁾ Plantar fasciitis causes significant discomfort and negatively impacts the health-related quality of life of affected individuals. Botulinum toxin was theorized over a decade ago to have potential efficacy in the management of plantar fasciitis.⁽²⁾ Botulinum toxins have been used as injectable agents in the management of refractory plantar fasciitis without complication and with demonstrable clinical efficacy.

[REDACTED]

This statistical analysis plan (SAP) describes the objectives of the study and the efficacy and safety assessments that are collected. The primary, secondary, and exploratory efficacy endpoints and the safety endpoints are defined, and the statistical methods used to analyze them are presented. Table shells for the planned end-of-text tables, figures, and listings are included following the text of the SAP.

[REDACTED]

[REDACTED]

[REDACTED]

2 STUDY OBJECTIVES

2.1 Primary Objective

The primary study objective is to compare the safety and efficacy of daxibotulinumtoxinA for injection versus placebo for managing plantar fasciitis as measured by the reduction in the visual analog scale (VAS) for pain for the foot at Week 8.

3 Overall Study Design and Plan

3.1 Study Design

The study is designed as a phase 2, prospective, randomized, placebo-controlled, double-blinded clinical trial to compare daxibotulinumtoxinA for injection and placebo injections for the management of plantar fasciitis signs and symptoms.

Approximately 60 subjects, from 5 sites in the United States, 18-65 years of age, [REDACTED]

[REDACTED]

[REDACTED]

[REDACTED]

[figure not shown]
The study duration for each participant is up to approximately five (5) months (up to four [4] weeks for Screening, a single Injection day, and up to 16 weeks of Follow-up). [REDACTED]

[figure not shown]
[REDACTED]

[figure not shown]
[REDACTED]

[REDACTED]

A participant is considered to have completed the study if he or she has completed all visits of the study including the last visit or the last scheduled procedure (See Table 3.1-1 for the complete schedule of assessments). The end of the study is defined as completion of the last visit or procedure in the trial globally.

[figure not shown]

3.1.1 Determination of Sample Size

With a total of 60 subjects (30 per group) and assuming a drop-out rate of no more than 20%, [REDACTED]

3.1.2 Treatments Administered

Approximately 60 adult subjects with a diagnosis of unilateral plantar fasciitis, refractory to conservative treatment, will be enrolled.

3.2 Efficacy and Safety Assessments

3.2.1 Efficacy Assessments

The efficacy assessments used in this study are:

- Visual Analog Scale (VAS) for Pain: The VAS for pain is a continuous scale self-completed by the respondent comprised of a horizontal or vertical line anchored by “no pain” (score of 0) and “worst pain” or “worst imaginable pain” (score of 100 [100-mm scale]).

■ [REDACTED]

■ [REDACTED]

■ [REDACTED]

■ [REDACTED]

■ [REDACTED]

3.2.2 Safety Assessments

Safety assessments include the physical examination; pregnancy testing for women of child-bearing potential (WOCBP); height, weight and other vital signs; 12-lead electrocardiograms; clinical laboratory evaluations; injection site evaluations, foot and ankle examinations, and assessments of adverse events.

3.2.2.1 Adverse Events

All adverse events (AEs) will be recorded and classified in accordance with MedDRA terminology. Severity, frequency, and relationship of AEs to study intervention will also be collected. AE severity will be graded as mild, moderate, or severe, as defined in Section 8.4.3.1 of the protocol. Relationship of an AE to investigational product will be assessed as definite, probable, possible, or unrelated, as defined in Section 8.4.3.2 of the protocol. AEs with an onset on or after the date and time of study treatment will be considered as Treatment-emergent.

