8.4 ADVERSE EVENTS AND SERIOUS ADVERSE EVENTS

8.4.1 DEFINITION OF ADVERSE EVENTS (AE)

For this protocol, an **adverse event (AE)** is any untoward medical occurrence (e.g., sign, symptom, disease, syndrome, intercurrent illness, clinically significant abnormal laboratory finding, injury or

accident) that emerges or worsens following administration of investigational product and until the end of trial participation that may not necessarily have a causal relationship to the administration of the investigational product. An AE can therefore be any unfavorable and/or unintended sign (including a clinically significant abnormal laboratory result), symptom, or disease temporally associated with the use of an investigational product, whether or not considered related to the investigational product. A treatment-emergent AE is one that occurs after any period of exposure to treatment.

Pre-existing conditions, which increase in frequency or severity or a change in nature as a consequence of an investigational product use will also be considered an adverse event.

An unexpected AE is an adverse reaction, the nature or severity of which is not consistent with the applicable product information (e.g., Investigator's Brochure for an unapproved investigational product or package insert/summary of product characteristics for an approved product).

Any clinically significant change in the study safety evaluations, (e.g., vital signs, laboratory results, ECG, injection site evaluation, physical/neurological examinations, etc.) post-treatment must be reported as an AE.

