8.4.4 TIME PERIOD AND FREQUENCY FOR EVENT ASSESSMENT AND FOLLOW-UP

The occurrence of an adverse event (AE) or serious adverse event (SAE) may come to the attention of study personnel during study visits and interviews of a study participant presenting for medical care, or upon review by a study monitor.

All AEs including local and systemic reactions not meeting the criteria for SAEs will be captured on the appropriate case report form (CRF). Information to be collected includes event description, time of onset, clinician's assessment of severity, relationship to study product (assessed only by those with the training and authority to make a diagnosis), and time of resolution/stabilization of the event. All AEs occurring while on study must be documented appropriately regardless of relationship. All AEs will be followed to adequate resolution.

Any medical condition that is present at the time that the participant is screened will be considered as baseline and not reported as an AE. However, if the study participant's condition deteriorates at any time during the study, it will be recorded as an AE.

Changes in the severity of an AE will be documented to allow an assessment of the duration of the event at each level of severity to be performed. AEs characterized as intermittent require documentation of onset and duration of each episode.

The Investigator or study staff will record all reportable events with start dates occurring any time after informed consent is obtained until 7 (for non-serious AEs) or 30 days (for SAEs) after the last day of study participation. At each study visit, the Investigator or study staff will inquire about the occurrence of

AE/SAEs since the last visit. Events will be followed for outcome information until resolution or stabilization.

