9.4 STATISTICAL ANALYSES

9.4.1 GENERAL APPROACH

All evaluable efficacy data will be included in the analysis following the intent-to-treat (ITT) principle. All subjects who received the study treatment (DaxibotulinumtoxinA for Injection or placebo) will comprise the modified-ITT population and will be grouped according to each subject's randomization assignment. The primary analysis will focus on the reduction from baseline in the VAS for pain at eight (8) weeks with missing data imputed by the last available value prior to the visit with missing value, that is, the last-observation-carried-forward (LOCF) approach. Analysis of covariate (ANCOVA) model including treatment group as a factor and baseline pain score as a covariate will be used.

Reductions from baseline VAS for pain for the foot over time up to eight (8) weeks will also be analyzed using a statistical method that handles repeated measures such as a generalized linear model (GLM) including treatment group, time (visit) and the treatment-visit interaction term as factors and the baseline VAS for pain as a covariates. For other secondary and exploratory efficacy outcome measures, appropriate statistical models (e.g., ANCOVA or GLM for continuous variables, and chi-squared/Fisher's

exact test or logistic regression for dichotomy or categorical variables) adjusting for relevant covariates will be employed to evaluate the treatment effect.

As a sensitivity analysis to check the impact of major protocol violations to study results, the primary and secondary efficacy outcome measures will also be analyzed on data from all subjects in per-protocol (PP) population, which consists of subjects in the modified-ITT population who do not have any major protocol violations. To check the robustness of results using the LOCF approach, different methods (such as observed data only or multiple imputation) may be employed to handle missing data when appropriate.

As an exploratory analysis, proportion of subjects achieving certain status defined by some efficacy assessments (e.g., having a reduction in the VAS for pain by a certain clinical meaning cut-point) will also be compared between treatment groups.

Safety data from all subjects who received study treatment will be summarized with subjects being grouped based on the treatment each subject actually received.

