4.1.4 Safety Population

All subjects who are randomized, receive treatment, and have provided at least one post-treatment safety assessment will be included in the Safety population. The summaries will be by documented treatment actually received.

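### The SAP's treatment-emergent rule looks only at onset, so an adverse event that starts between consent and injection and worsens afterwards can be left out of the TEAE tables

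*SAP*

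**What the plan says.** **Treatment-emergent events.** SAP 3.2.2.1 gives one criterion: "AEs with an onset on or after the date and time of study treatment will be considered as Treatment-emergent". No readable SAP text adds worsening to it. SAP 4.7.2 builds the tables by system organ class, preferred term, severity, relationship and seriousness on TEAEs. It compares the arms on the frequency of subjects with at least one TEAE, to Week 8 and over the whole trial. The same section lists every adverse event by subject, treatment-emergent or not.

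**Adverse events in the protocol.** Protocol 8.4.1 defines an adverse event as an untoward occurrence "that emerges or worsens following administration of investigational product and until the end of trial participation". It also brings in "Pre-existing conditions, which increase in frequency or severity or a change in nature as a consequence of an investigational product use". Its own sentence on treatment emergence is shorter: "A treatment-emergent AE is one that occurs after any period of exposure to treatment".

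**Recording.** Protocol 8.4.4 collects events with start dates from informed consent onwards. It treats a condition present at screening as baseline and records an adverse event if that condition deteriorates. It also says "Changes in the severity of an AE will be documented", so that time at each severity level can be assessed.

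**Who is summarised.** SAP 4.1.4 says that randomised and treated subjects who "have provided at least one post-treatment safety assessment will be included in the Safety population". Protocol 9.4.1 has no such condition: "Safety data from all subjects who received study treatment will be summarized", by treatment actually received.

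**The concern.** The SAP's criterion carries over the first half of the protocol's adverse event definition (new events) and leaves out the second (worsening). This matters only for events already open at injection, and the protocol's recording rules allow such events to be in the database.

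Safety is part of the primary objective, and the TEAE tables are the main between-arm safety output. Everyone enters with persistent heel pain, and the treatment concept includes transient partial paralysis of the calf complex, so local worsening is a plausible kind of harm. If active treatment made open events worse and those events were left out, the comparison would be pulled towards no difference. Where the start date is left to the site, two sites could also classify the same clinical course differently while both follow the protocol.

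**Working it through.** There is no stated figure to reproduce. The check takes each possible course of an event through the recording rules and then through the SAP criterion.

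**Inputs**
- TEAE criterion: onset at or after injection (SAP 3.2.2.1).
- Adverse event definition: new or worsening after injection (protocol 8.4.1).
- Collection from consent; deterioration of a screening condition recorded as an adverse event; severity changes documented (protocol 8.4.4).
- Screening of up to four weeks (protocol 4.5).
- Planned arm size: 30 (protocol 9.2, SAP 3.1.1).

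**Cases**

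| Case | Course and recording | Meets the SAP criterion? |
|---|---|---|
| A | New event after injection | Yes |
| B | Condition present at screening deteriorates after injection; event dated from the deterioration | Yes |
| C | As B, but the condition's original start date is entered | No |
| D | Event starts between consent and injection, worsens after injection; same record with a severity change | No |
| E | As D, but a new record is opened at the worsening | Yes |

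Cases B and C describe the same clinical course, as do D and E. Only the recording differs, and the readable text does not settle it. For B and C, protocol 8.4.4 says that deterioration is recorded but not which start date to enter; B is the natural reading. For D and E, it describes one event passing through several severity levels, which points to D. Case D is therefore the main gap, and its window is at most about four weeks per subject.

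**Where the lost events go.** A case C or D event stays in the by-subject listing. It is absent from the TEAE tables and from the between-group comparison. The SAE summary sentence in SAP 4.7.2 is not limited to TEAEs, so an event that becomes serious may still be tabulated there.

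**Scale.** One subject in an arm of 30 is 1/30 = 3.3 percentage points of that arm's incidence. This holds only if the subject has no other TEAE (or, for one table row, no other TEAE in that row). The number of such subjects cannot be derived: the documents give no rate of events open at injection and no rate of worsening.

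**Safety population.** SAP 4.1.4 removes subjects, not events. Adverse events (protocol 8.3) and injection sites (SAP 3.2.2.6) are both assessed after treatment on the injection day, so nearly every treated subject qualifies. If one did not, the denominator would fall from 30 to 29. With an assumed 6 subjects with events, 6/30 = 20.0% becomes 6/29 = 20.7%, which is 0.7 points higher.

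**The case against.** A reader might infer that the SAP contradicts the protocol. It does not. The protocol's own TEAE sentence has no worsening clause either, and the SAP criterion follows it. The SAP is narrower than the protocol's adverse event definition, which is a weaker statement.

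A reader might also infer that worsening of the heel pain everyone brings to the trial is lost. The documents do not support that. Protocol 8.4.4 treats such a condition as baseline with no adverse event record, and its deterioration is a new adverse event. Protocol 8.3 likewise sends significant examination findings present before administration to the medical history page. Dated naturally, the deterioration falls after injection and counts. The same route could absorb some findings that arise between consent and injection, which narrows case D. It does not close it, because 8.4.4 still calls for reportable events from consent onwards. Muscle weakness is also more likely to be new than worsened, since neuromuscular disease and systemic muscle weakness are exclusions.

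Local harm is visible elsewhere too. Injection-site findings are tabulated by arm and visit, motor strength and pain location are examined at each follow-up visit, and foot pain on the VAS is the primary endpoint.

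Finally, text is redacted in SAP 4.7.2 and 4.8.4 (data handling conventions), where an onset-date or worsening rule would commonly sit. Its absence cannot be confirmed.

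All of this stands, and it limits the point to case D plus an unstated dating convention. It does not remove the point: SAP 3.2.2.1 reads as a complete definition and refers to no other rule.

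**Conclusion.** As readable, the SAP's TEAE criterion is narrower than the protocol's adverse event definition. An event that starts between consent and injection and then worsens can be left out of the TEAE summaries and the between-group comparison, while remaining in the full listing. A screening condition that deteriorates is captured if dated from the deterioration, but no readable text says that it must be.

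The size is unknown: 3.3 percentage points of an arm's incidence for each affected subject with no other TEAE, at the planned 30 per arm. The conclusion assumes that sites keep one record per event when severity changes, and that the redacted text holds no worsening or onset-date rule. The documents support saying that the tables can understate worsening. They do not support saying that local harm will be understated, or by how much.

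The Safety-population mismatch is real but separate. It cannot make a worsened event drop out, because a subject with a reported post-treatment event has already been assessed after treatment. Its expected effect is about nil and, if anything, raises incidence slightly.

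**What to change.** 1. **SAP 3.2.2.1.** Define a TEAE as an adverse event that starts, or that increases in severity or frequency or becomes serious, on or after the injection date and time. If a redacted section already says this, cite it here.
2. **Dating convention.** State that deterioration of a pre-existing condition is dated from the deterioration. For an event already open at injection, derive the flag from the severity changes and episode dates that protocol 8.4.4 already requires.
3. **SAP 4.1.4 (separate and minor).** Define the Safety population as every treated subject, grouped by treatment received, to match protocol 9.4.1.

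The cost is a few SAP sentences and one extra programming flag, with no change to the design or to the data that the protocol asks for. TEAE counts may come out slightly higher.
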